20. Female subjects who are pregnant, breast-feeding or male or female patients of reproductive potential who are not employing an effective method of birth control.
21. Any condition that, in the opinion of the investigator, would interfere with evaluation of study treatment or interpretation of patient safety or study results.
22. Subjects with uncontrolled seizures.

23. Symptomatic or uncontrolled brain metastases requiring concurrent treatment, inclusive of but not limited to surgery, radiation and/or corticosteroids.

Investigational Product(s), Dose and Mode of Administration:

Durvalumab will be given at 1500 mg Q4W (equivalent to 20 mg/kg Q4W) IV infusion for 12 months. Population PK analysis indicated only minor impact of body weight (WT) on PK of durvalumab (coefficient of ≤ 0.5). Please refer to fixed dose under 1.2.2 for details.

Study Assessments and Criteria for Evaluation:

Safety Assessments: Adverse events and toxicity will be captured with CTCAE version 4.03. Based on the generally healthy condition of patients with stage 0is or stage I (with Cis component), we do not anticipate significant toxicities. The study will also be stopped early if 3 or more subjects in the first 10 subjects developed SAEs attributed to Durvalumab.

Efficacy Assessments:

Complete response rate at month 6 as determined by mapping biopsy at month 6 during treatment with Durvalumab.

Complete response rate at year 2 as determined by mapping biopsy at year 2 after 1 year of Durvalumab.

Statistical Methods and Data Analysis:

Statistical analysis for the primary and secondary endpoints will be descriptive.

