1.5 Benefit/risk and ethical assessment

As described in section 1.2.2, Durvalumab is well tolerated in human subjects. No tumor types appeared to be associated with unique AEs. Immune-related AEs (irAEs), which are important risks of immune checkpoint inhibitors, have been observed with Durvalumab and include colitis, pneumonitis, hepatitis/hepatotoxicity, neuropathy/neuromuscular toxicity, endocrinopathy, dermatitis, and nephritis. These irAEs are not that different than the anti-PD1 or anti-PDL1 agents being approved by FDA for treating melanoma, kidney cancer and non-small cell lung cancer.

Due to the lack of effective intravesical treatment for BCG refractory urothelial carcinoma in situ (CIS) of the bladder, radical cystectomy is often recommended. If subject's CIS of bladder does not respond to IV Durvalumab, delaying cystectomy could lead to cancer progression to the muscle invasive or even metastatic stage. The protocol therefore mandates a baseline staging work up prior to study enrollment and every 3 months cystoscopy with mapping biopsy during the 2 year study period. For subjects who elect bladder preservation for their CIS of bladder, it is a common practice to do every 3 months surveillance cystoscopy till at least a year after completing the intravesical therapy. We don't anticipate adding IV Durvalumab will increase the risks or complications of routine cystoscopy with mapping biopsy. For subjects whose CIS of bladder responded Durvalumab, Durvalumab may provide an alternative treatment that leads to bladder preservation.

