3.3 Study Oversight for Safety Evaluation

DMC at Moffitt Cancer Center will monitor this phase 2 study initiated by Moffitt's investigator. The study will be stopped early if there are 3 or fewer responses in the first 13 patients in the stage I of Simon 2 stage design. The study will also be stopped early if 3 or more subjects of the first 10 subjects developed SAEs attributed to Durvalumab.

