10.3 Recording of adverse events and serious adverse events

Adverse events will be recorded using a recognized medical term or diagnosis that accurately reflects the event and captured in OnCore. Adverse events will be assessed by the investigator for severity, relationship to the investigational product, possible etiologies, and whether the event meets criteria of an SAE and therefore requires immediate notification to AstraZeneca/MedImmune Patient Safety.

The following variables will be collected for each AE:

- AE (verbatim)
- The date when the AE started and stopped
- Changes in NCI CTCAE grade and the maximum CTC grade attained
- Whether the AE is serious or not
- Investigator causality rating against durvalumab
- Action taken with regard to durvalumab /comparator/combination agent
- Outcome

In addition, the following variables will be collected for SAEs as applicable:

- Date AE met criteria for serious AE
- Date Investigator became aware of serious AE
- AE is serious due to <<criteria>>
- Date of hospitalization
- Date of discharge
- Probable cause of death
- Date of death
- Autopsy performed
- Description of AE
- Causality assessment in relation to Study procedure(s)

Events, which are unequivocally due to disease progression, should not be reported as an AE during the study. Disease progression can be considered as a worsening of a patient's condition attributable to the disease for which the investigational product is being studied. It may be an increase in the severity of the disease under study and/or increases in the symptoms of the disease. The development of new metastasis of the primary cancer under study should be considered as disease progression and not an AE.

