11.2 Methods of statistical analyses

The null hypothesis that the 18% historical complete response rate at month 6 will be tested against a one-sided alternative of 40% or higher complete response rate with Durvalumab at month 6 in BCG refractory CIS of bladder. We use a Simon's two-stage design (Simon, 1989) based on the optimal two-stage designs and admissible designs (Jung et al. 2004) for Phase II single arm clinical trials.

In the first stage of this study plan, 13 patients will be accrued. If there are 3 or fewer responses in these 13 patients, the study will be stopped. Otherwise, 21 additional patients will be accrued for a total of 34. The null hypothesis will be rejected if 9 or more responses are observed in 34 patients. In summary 34 is the total number of subjects required, 13 is the number of subjects accrued during stage 1, if 3 or fewer responses are observed during stage 1, the trial is stopped early for futility, and, if 9 or fewer responses are observed by the end of stage two, then no further investigation of the drug is warranted. This design yields a one-sided type I error rate of 0.047 and power of 80% when the true response rate is 40%.

The primary analysis will be performed for the (complete) response rate based on month 6 mapping biopsy. We will use an exact probability method such as Chi-square and binomial tests.

n	n ₁	r ₁	r ₂	Type 1 Error	Power	EN ₀	Probability of early stopping	Interval for w	Comment
34	13	3	9	0.0473	0.8031	17.1	0.8061	[0,0.1243]	Optimal

*EN*₀ is the expected sample size for the trial when response rate is p0

Interval for w is the set of values w such that the design minimizes $w * 2I + (1 - w) * EN0$

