11.3 Determination of sample size

The required total number of subjects is 34. 13 is the number of subjects accrued during stage 1. If 3 or fewer responses are observed during stage 1, the trial is stopped early for futility. If 9 or fewer responses of total 34 patients are observed by the end of stage two, then no further investigation of the drug is warranted. This design yields a one-sided type I error rate of 0.047 and power of 80% when the true response rate is 40% based on Simon's optimal two-stage design.

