13.2 Monitoring of the study

The protocol monitoring committee (PMC) at Moffitt cancer center meets once a month. The PMC reviews and evaluates safety and/or efficacy data for all physician authored clinical intervention trials. The PMC ensures the safety of patients and the validity and integrity of data. PMC reviews SAEs, deviations, Interim analysis, interim and final reports from the external Data Monitoring Committee (DMC) as well as audits both internally and externally.

Clinical Study Protocol

Drug Substance Durvalumab (Medi4736)

Study Number MCC 18788/MCC18788/ESR-15-11326

Edition Number 1.9.4

Date 10/08/2018

The PMC can make the following determinations, Accepted, Acceptable with Corrective Action and Tabled.

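### The only prespecified study-level safety trigger counts the first 10 subjects; none is stated for subjects 11 to 34, and no count of progression is planned

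*Combined protocol and SAP*

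**What the plan says.** The safety stop appears twice with the same content. Section 3.3 has "The study will also be stopped early if 3 or more subjects of the first 10 subjects developed SAEs attributed to Durvalumab", and the synopsis (Safety Assessments) has "The study will also be stopped early if 3 or more subjects in the first 10 subjects developed SAEs attributed to Durvalumab". No operating characteristics are given for it.

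The planned size is in 11.3: "The required total number of subjects is 34. 13 is the number of subjects accrued during stage 1". Under 4.4, subjects withdrawn before the month 6 mapping biopsy are replaced, so the number treated can exceed 34. The only other study-level stop is the stage 1 futility rule. The safety analysis in 11.2.1 is descriptive, and the interim analysis section deals only with responses.

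On oversight, 3.1 and 3.3 assign monitoring to a DMC at the sponsor's centre. Section 13.2 describes a protocol monitoring committee (PMC) that meets monthly and reviews SAEs, and then says: "The PMC can make the following determinations, Accepted, Acceptable with Corrective Action and Tabled". Section 14.2 adds ongoing safety monitoring by the drug company.

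On progression, 1.5 warns that for a subject who does not respond "delaying cystectomy could lead to cancer progression to the muscle invasive or even metastatic stage". Section 10.3 states: "Events, which are unequivocally due to disease progression, should not be reported as an AE during the study". Under 10.3.3 a death clearly due to progression is documented but is not an SAE. Sections 3.1 and 9 take a subject off study when a biopsy shows muscle-invasive disease. Appendices C and D collect later anticancer therapy, survival and discretionary imaging.

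**The concern.** A rule confined to the first 10 subjects uses less than a third of the safety information the trial will gather. If two of those 10 have an attributed SAE, no number of events in the remaining subjects can meet the criterion. Action then rests on committee judgement with no stated threshold, and the one list of committee decisions in the protocol does not mention suspension or stopping.

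The progression point is separate. Subjects in this trial postpone cystectomy, and the protocol itself says what that postponement may cost. Events unequivocally due to progression are not AEs, so they cannot count towards the rule, and no other table or review is planned to bring them together. A final report could describe tolerability accurately and still leave out the count a reader needs to judge whether the delay was acceptable.

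**Working it through.** **Inputs.** Trigger 3 of 10 (3.3, synopsis). Total 34 and stage 1 size 13 (11.3). Stage 1 futility at 3 or fewer responses, with response rates 18% and 40% (11.2). The documents' only overall rate of drug-related SAEs is 9 of 303 in the lung cancer study in 1.2.2: 9/303 = 3.0%. All other true SAE rates below are assumptions, shown as a range.

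**1. The plan's own figures.** The safety rule has none to reproduce. The two-stage design has, and its early-stopping probability is needed in step 5. With X1 ~ Bin(13, p), P(X1 ≤ 3) = 0.8061 at p = 0.18, which matches the table in 11.2. Type I error 0.0473, power 0.8031 and expected size 17.07 also match. At p = 0.40, P(X1 ≤ 3) = 0.1686. Stage 1 is therefore passed with probability 1 − 0.8061 = 0.1939 at 18% response and 1 − 0.1686 = 0.8314 at 40%.

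**2. Coverage.** 34 − 10 = 24 subjects (24/34 = 71%) lie outside the rule. This is a minimum because of replacements. In the extreme case, 2 + 24 = 26 of 34 (76%) could have an attributed SAE without meeting the criterion.

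**3. The present rule.** P(stop) = P(X ≥ 3), X ~ Bin(10, p). At p = 0.30 this is 1 − 0.3828 = 0.6172, so the check is passed 38% of the time. About 24 × 0.30 = 7.2 attributed-SAE subjects would then be expected among the other 24, if all are enrolled.

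**4. The same proportion carried forward.** Stop at 3 or more of 10, 6 or more of 20, or 9 or more of 30. The exact calculation adds one subject at a time and removes paths that have already crossed a boundary. Cumulative stopping probability with full enrolment:

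| True rate | Look at 10 (present rule) | By 20 | By 30 |
|---|---|---|---|
| 3.0% | 0.0027 | 0.0027 | 0.0027 |
| 10% | 0.0702 | 0.0734 | 0.0737 |
| 20% | 0.3222 | 0.3682 | 0.3851 |
| 30% | 0.6172 | 0.7186 | 0.7671 |
| 40% | 0.8327 | 0.9232 | 0.9574 |

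**5. Allowing for the futility stop.** The looks at 20 and 30 happen only if stage 1 is passed. If SAE and response are independent, P(stop for safety) = P(stop at 10) + P(pass stage 1) × [P(stop by 30) − P(stop at 10)]. At a 30% SAE rate the bracket is 0.7671 − 0.6172 = 0.1499.

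- Response 18%: 0.6172 + 0.1939 × 0.1499 = 0.646.
- Response 40%: 0.6172 + 0.8314 × 0.1499 = 0.742.

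These calculations treat each subject's SAE status as known at the look. The present rule does not say when that is.

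**6. Progression, passages side by side.** Section 1.5 names the risk. Section 10.3 keeps events unequivocally due to it out of AEs, and 10.3.3 keeps deaths clearly due to it out of SAEs. T2 on an on-study biopsy is documented and ends participation. The planned analyses in 11.2 list no progression count. Appendices C and D have no item for stage at a later cystectomy. The futility rule does not stand in for this: it looks once, at 13 subjects. Response in 9.1.1 is absence of CIS on mapping biopsies. Subjects withdrawn before month 6, who could include early progressors, are replaced under 4.4.

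**The case against.** The strongest reply is that later subjects are watched. The DMC monitors the study, the PMC sees SAEs monthly, the drug company reviews safety continuously, and individual discontinuation rules apply throughout. The rule has no time limit, so the first 10 subjects can still trigger it late in follow-up. This stands. A reader might infer that safety is never examined again after subject 10, and the documents do not support that. Nor do they show that nobody can stop the trial: 13.2 lists PMC determinations rather than DMC powers, and corrective action is not defined to exclude suspension. What is missing is a stated criterion and a stated power.

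Second, rates of 20 to 40% are far above the documents' evidence: 3% related SAEs in the lung cancer study, and 9.4% of 694 subjects with related events of grade 3 or higher in Study 1108. Those are other populations and dosing schedules, but they make a front-loaded rule in a small phase 2 trial defensible. They also mean that the added looks cost almost nothing if the drug behaves as expected.

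Third, the look at 30 comes with only 4 planned subjects left to enrol, and the futility stop often prevents the later looks. Both are correct, and step 5 accounts for the second.

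Fourth, on-study progression is not lost. T2 biopsies and progression deaths are documented, and the appendices include imaging tied to T2. That also stands, and it narrows the point to the missing count and the uncollected later stage.

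**Conclusion.** The point holds as a limited, inexpensive improvement. No prespecified study-level safety criterion covers at least 24 of 34 subjects. Extending the rule raises the stopping probability at an assumed 30% rate from 0.62 to 0.77 with full enrolment, or to between 0.65 and 0.74 once futility stopping is counted. This assumes independence of SAE and response, and complete SAE status at each look.

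Four stronger readings should be avoided.

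- Three in 10 is a count. The documents do not declare 30% a tolerated rate, and the proportion is carried forward here only for consistency.
- Section 1.5 names progression as a risk but does not rank it as the main one.
- One might multiply 34 by the non-response rates and infer that 20 to 28 subjects leave at month 6. That ignores the futility rule. With expected sizes of 17.07 and 13 + 0.8314 × 21 = 30.46, the expected non-responders number about 17.07 × 0.82 = 14 at 18% response and 30.46 × 0.60 = 18 at 40%.
- Progression is not unrecorded. It lacks a planned summary and, after study exit, a stage.

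**What to change.** **Safety trigger.** In 3.3 and the synopsis, keep the present event definition and carry the proportion forward over treated subjects, for example 3 or more of 10, 6 or more of 20 and 9 or more of 30. State when a subject counts as observed at each look. In 13.2, state that the monitoring committee can suspend or stop the study. Do not widen the event from attributed to at least possibly related, the term that 4.3 and 6.3 use for individual discontinuation. That would raise the counted rate by an unknown amount, and the figures above would no longer apply.

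**Progression.** In 11.2.1, add the number of subjects in whom T2 or above or metastatic disease is newly detected, each subject counted once, and give the running count to the monitoring committee. Add stage from any standard-of-care cystectomy learned at the follow-up contacts already in Appendices C and D.

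**Cost.** Amendment wording and one added data field, with no new visits or procedures. The statistical cost is a slightly higher false-stop chance: 0.070 to 0.074 at a true rate of 10%, and about 0.003 either way at 3%.

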4. SUBJECT SELECTION

4.1 Inclusion criteria

For inclusion in the study subjects must fulfill all of the following criteria:

1. Age \geq 18 years at the time of screening.
2. Must have pathologically confirmed urothelial carcinoma in situ (CIS) of the bladder and meet one of the following criteria.
 1. Persistence of high-grade CIS at 6 months following an adequate course of BCG; OR
 2. Stage/grade progression at 3 months after induction BCG; OR
 3. Recurrence of high-grade CIS after achieving a disease-free state (i.e., CR) following induction of an adequate course of BCG that occurs < 9 months after the last exposure to BCG; OR
 4. Persistent CIS noted on the bladder biopsies within 3 months of completing at least 2 induction BCG (minimum of five weekly instillations).

An adequate course of BCG should be defined as at least one course of induction (minimum of five weekly instillations) and one maintenance (two of three instillations) in a 6 months period, with an exception for any patient with grade/stage progression after induction BCG (minimum of five weekly instillations).

3. ECOG performance status of 0-1.
4. Adequate organ and marrow function, as defined as:
 - Haemoglobin ≥ 9.0 g/dL, Absolute neutrophil count (ANC) $\geq 1.5 \times 10^9/L$ (≥ 1500 per mm 3), and Platelet count $\geq 100 \times 10^9/L$ ($\geq 100,000$ per mm 3)

- AST (SGOT)/ALT (SGPT) \leq 2.5 x institutional upper limit of normal Serum bilirubin \leq 1.5 x institutional upper limit of normal (ULN).
- Serum creatinine CL $>$ 40 mL/min by the Cockcroft-Gault formula (Cockcroft and Gault 1976) or by 24-hour urine collection for determination of creatinine clearance:

Males:

$$\text{Creatinine CL} = \frac{\text{Weight (kg)} \times (140 - \text{Age})}{72 \times \text{serum creatinine (mg/dL)}}$$

Females:

$$\text{Creatinine CL} = \frac{\text{Weight (kg)} \times (140 - \text{Age})}{72 \times \text{serum creatinine (mg/dL)}} \times 0.85$$

5. Written informed consent and any locally required authorization (e.g., HIPAA in the USA) obtained from the subject prior to performing any protocol-related procedures, including screening evaluations.
6. Female subjects must not be pregnant, or breast feeding and must have a negative urine or serum pregnancy test within 28 days prior to treatment on day 1. Females of childbearing potential who are sexually active with a non-sterilized male partner must use a highly effective method of contraception from the time of screening, and must agree to continue using such precautions for 90 days after the final dose of Durvalumab. They must also refrain from egg cell donation for 90 days after the final dose of Durvalumab.
7. Non-sterilized males who are sexually active with a female partner of childbearing potential must use a highly effective method of contraception and refrain from sperm donation from Day 1 through 90 days after receipt of the final dose of Durvalumab.

4.2 Exclusion criteria

Subjects should not enter the study if any of the following exclusion criteria are fulfilled:

1. Muscle invasive (T2 or above) urothelial carcinoma or urothelial carcinoma outside the bladder.
2. Involvement in the planning and/or conduct of the study (applies to both AstraZeneca staff and/or staff at the study site) or previous enrolment in the present study.
3. Participation in another clinical study with an investigational product during the last 4 weeks.
4. Any previous treatment with a PD1 or PD-L1 inhibitor, including durvalumab.
5. History of another primary malignancy except for:
 - Malignancy treated with curative intent and with no known active disease ≥ 3 years before the first dose of study drug and of low potential risk for recurrence.
 - Adequately treated non-melanoma skin cancer or lentigo maligna without evidence of disease.
 - Adequately treated carcinoma in situ without evidence of disease eg, cervical cancer in situ.
6. Receipt of the last dose of anti-cancer therapy (chemotherapy, immunotherapy, endocrine therapy, tyrosine kinase inhibitor, biologic therapy, tumor embolization, monoclonal antibodies, other investigational agent) ≤ 30 days prior to the first dose of study drug and within 6 weeks for nitrosourea, mitomycin C or intravesicle therapy).
7. Mean QT interval corrected for heart rate (QTc) ≥ 470 ms calculated from 3 electrocardiograms (ECGs) using Frediricia's Correction.
8. Current or prior use of immunosuppressive medication within 28 days before the first dose of durvalumab, with the exceptions of intranasal and inhaled corticosteroids or systemic corticosteroids at physiological doses, which are not to exceed 10 mg/day of prednisone, or an equivalent corticosteroid.
9. Any unresolved toxicity (CTCAE grade 2 or above) from previous anti-cancer therapy.
<<Subjects with irreversible toxicity that is not reasonably expected to be exacerbated by the investigational product may be included (e.g., hearing loss, peripherally neuropathy)>>

10. Any prior Grade ≥ 3 immune-related adverse event (irAE) while receiving any previous immunotherapy agent, or any unresolved irAE $>$ Grade 1.
11. Active or prior documented autoimmune disease within the past 2 years
NOTE: Subjects with vitiligo, Grave's disease, or psoriasis not requiring systemic treatment (within the past 2 years) are not excluded.
12. Active or prior documented inflammatory bowel disease (e.g., Crohn's disease, ulcerative colitis).
13. History of primary immunodeficiency.
14. History of allogeneic organ transplant.
15. History of pneumonitis.
16. History of hypersensitivity to durvalumab or any excipient.
17. Uncontrolled intercurrent illness including, but not limited to, ongoing or active infection, symptomatic congestive heart failure, uncontrolled hypertension, unstable angina pectoris, cardiac arrhythmia, active peptic ulcer disease or gastritis, active bleeding diatheses including any subject with confirmed acute or chronic hepatitis B, hepatitis C or human immunodeficiency virus (HIV), or psychiatric illness/social situations that would limit compliance with study requirements or compromise the ability of the subject to give written informed consent.
18. Known history of previous clinical diagnosis of tuberculosis.
19. Receipt of live attenuated vaccination within 30 days prior to study entry or within 30 days of receiving durvalumab.
20. Female subjects who are pregnant, breast-feeding or male or female patients of reproductive potential who are not employing an effective method of birth control.
21. Any condition that, in the opinion of the investigator, would interfere with evaluation of study treatment or interpretation of patient safety or study results.
22. Subjects with uncontrolled seizures.
23. Symptomatic or uncontrolled brain metastases requiring concurrent treatment, inclusive of but not limited to surgery, radiation and/or corticosteroids.

